When a patient treated with valsartan/sacubitril (Entresto[®]) is considered for randomization in to the trial, only NT-proBNP, and not BNP, should be assessed during the screening phase.

As reported in the SmPC (Summary of Product Characteristics) of Entresto[®], BNP is not a suitable biomarker of heart failure in patients treated with Entresto[®] because BNP is a neprilysin substrate. NT-proBNP is not a neprilysin substrate and is therefore a more suitable biomarker.

This specification relates only to the assessment method but does not affect the inclusion criterion.

Treatment Blinding

The previous versions of the protocol did not explain which study roles are blinded and which are unblinded. The current amendment clarifies that the clinical trial team (e.g. Clinical Trial Lead, Clinical Trial Manager, Medical Lead, Trial Statistician) are blinded throughout the study and that only roles specifically mentioned in the Safety Manual are unblinded.

Study Status

The recruitment in the study is ongoing.

So far, more than two thousand three hundred and thirty (2337) patients have been randomized by Austria, Belgium, Bulgaria, Croatia, Czech Republic, Estonia, Finland, France, Germany, Greece, Hungary, Iceland, Italy, Latvia, Lithuania, Poland, Portugal, Romania, Russia, Serbia, Slovakia, Slovenia, Spain, Switzerland and United Kingdom in the study.

Changes to specific sections of the protocol are shown in the track changes version of the protocol using ~~strike through red font for deletions~~ and red underlined for insertions. A copy of this amended protocol will be sent to the Institutional Review Board (IRBs)/Independent Ethics Committee (IECs) and Health Authorities.

The changes described in this amended protocol require IRB/IEC approval prior to implementation. The changes herein affect the Informed Consent. Sites are required to update and submit for approval a revised Informed Consent that takes into account the changes described in this protocol amendment.

Changes to the protocol

Section 4.1 and Table 6.1 updated to clarify that only NT-proBNP should be assessed in patients under valsartan/sacubitril (Entresto®) therapy

Section 5.4 updated to clarify the management of the treatment blinding in the study

Section 6.5.4 updated to clarify the volume of the blood sample collection.

Section 7 updated to clarify the correct reporting of Worsening of Heart Failure events versus Adverse Events.

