6.5 Safety

Safety will be assessed by comparing the serelaxin group to the standard of care only group with regard to the frequency of AEs/SAEs, changes in vital signs, physical examination findings, and clinical laboratory test results (chemistry, hematology, and urinalysis). All non-serious AEs will be collected through Day 5 and SAEs (regardless of causality) through Day 14. Any SAEs experienced after Day 14 should be reported to Novartis only if the investigator suspects a causal relationship to study treatment.

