6.6.6 Echocardiography

Echocardiography evaluation is not a mandatory requirement of the protocol; in case the evaluation is performed and the values obtained are available in the source documents, they need to be entered into eCRF. Most recent data up to the last 12 months can be entered.

7 Safety monitoring

All AEs will be collected through Day 5, and all serious adverse events will be collected through Day 14, regardless of suspected causality. After Day 14 only suspected SAEs will be collected and databased.

Specific handling of the Study Endpoint WHF:

WHF events should be recorded not only as an endpoint but systematically as an AE as well. All WHF endpoints should thus be reported as AEs/SAEs in the AE eCRF page.

Non-serious WHF event should be reported through Day 5 and serious (SAE) WHFs should be reported through Day 14. After Day 14, only those study endpoints that qualify for SAEs and are also suspected to be related to the study medication should be reported in the AE eCRF page. It is recommended but not mandatory that the same verbatim should be used for an individual event for both the endpoint reporting and the AE reporting, i.e. "Worsening of Heart Failure".

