5.3. SAFETY DATA

All the safety analyses will be done on the Safety set.

Adverse events

The incidence of Adverse Events (AEs) recorded through Day 5 and Serious Adverse Events (SAEs) recorded through Day 14 will be presented for the Safety set. Treatment emergent AEs/SAEs will be considered as those AEs/SAEs with an onset date and time after treatment initiation for the serelaxin group. For the Standard of Care Only group, date and time of randomization will be considered as treatment initiation. In case of missing time of onset of the event, only the onset date will be used for the evaluation of the incidence of the AE. Adverse events with an onset between informed consent and treatment initiation will be listed separately.

Tables reporting general summary of AEs will be produced by treatment group specifying the number of total events and absolute and relative frequency of patients with AEs. As a patient may have more than one AE, the total number of AEs could be greater than the total number of patients. Further summaries by treatment group will be produced for non-serious AE and serious AE by time period, e.g., through Day 5 and through Day 14.

Absolute and relative frequency of patients with drug-related AEs, severe AEs, SAEs, AEs with an outcome of death, AEs leading to permanent discontinuation of treatment, AEs indicative of safety risk and events of interest (please refer to the section below for the definition of safety risk events and events of interest) will also be reported for treatment emergent AEs. The number of distinct adverse events by low level term will be provided. Drug-related AEs will be the AEs with relationship to study treatment equal to “Yes”, “Yes, investigational treatment”, “Yes, other study treatment (not-investigational)”, “Yes, both and/or indistinguishable”; if the

	Statistical Analysis Plan
	Sponsor: NOVARTIS Protocol number: CRLX030A3301

relationship to study drug is unknown or missing, the AE will be considered to be drug-related as well. eCRF severe events will be considered as severe events in the analysis. These summaries will be repeated for treatment emergent SAEs.

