Treatment emergent AEs will be tabulated by System Organ Class (SOC) and Preferred Term (sorted in alphabetical order within each SOC) using the latest MedDRA dictionary, and by System Organ Class, Preferred Term and severity. Absolute and relative frequency of patients who have experienced each type of event will be presented; if the same patient reported more than one occurrence of the same AE with different intensity, the worst reported severity grade for each event for the patient will be used for the analysis. The most frequent treatment emergent AEs will also be tabulated by Preferred Term sorted by descending frequency for AEs with an incidence rate of at least 5% in the serelaxin group.

In addition, treatment emergent adverse events associated with

- worsening heart failure (WHF)/all cause death through Day 5
- confirmed systolic blood pressure decrease event (CBPDE)

will be summarized by system organ class and preferred term. These AEs are determined by taking the answer “Yes” to the questions “Does AE meet the definition of Endpoint?” and “Does AE meet the definition of Systolic Blood Pressure Decrease Event?”, respectively.

Treatment emergent SAEs will be summarized similarly. Treatment emergent SAEs will be summarized by time period of onset, i.e., through Day 5 and through Day 14. Treatment emergent SAEs are defined as those which start after treatment start for serelaxin group, or after randomization for Standard of Care group.

All study-drug-related AEs, AEs with an outcome of death, AEs leading to permanent discontinuation of treatment will be listed with all their details. Time from the treatment start for serelaxin group or from randomization for Standard of Care group, to the AE start/end date, will be also computed. Elapsed days, hours and minutes plus 1 minute will be reported on the listing.

In case of an ongoing event, no days relative to the end of the event will be computed.

In case of missing time of start or end of an event, no relative days will be computed.

Safety risks and events of interest

Adverse events will be also presented according to the search strategies using the latest MedDRA dictionary version available before database lock, as specified in the Case Retrieval Strategy (CRS) defined by Novartis. Adverse events will be characterized as safety risks and as events of interest according to the rules specified in Table 5.3-1 and Table 5.3-2, respectively.

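### The overall any-AE, any-SAE and severe-AE comparisons contain the WHF efficacy events, and the SAP plans no version without them

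*Protocol*

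**What the plan says.** **Recording.** Protocol section 7, in its paragraph on the WHF endpoint, says that "WHF events should be recorded not only as an endpoint but systematically as an AE as well" and that "All WHF endpoints should thus be reported as AEs/SAEs in the AE eCRF page". The windows are: "Non-serious WHF event should be reported through Day 5 and serious (SAE) WHFs should be reported through Day 14". After Day 14 only serious events suspected to be drug-related are reported. The wording of the AE entry is left open: "It is recommended but not mandatory that the same verbatim should be used for an individual event".

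**Comparison.** Protocol section 6.5 states that "Safety will be assessed by comparing the serelaxin group to the standard of care only group with regard to the frequency of AEs/SAEs", together with vital signs, physical examination and laboratory results.

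**Analysis.** SAP section 5.3 summarizes AEs through Day 5 and SAEs through Day 14 in the Safety set. It counts patients with any AE by arm, and then "Absolute and relative frequency of patients with drug-related AEs, severe AEs, SAEs" and further categories among treatment-emergent events. Nothing in the section removes endpoint events from these counts.

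**What else is tabulated.** The same section gives tables by system organ class, preferred term and severity. It also gives a separate by-term table of AEs answered yes to "Does AE meet the definition of Endpoint", described as WHF or death through Day 5, and tables of safety risks and events of interest through Day 5 and Day 14.

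**Who decides.** Under SAP section 5.2 only committee-confirmed events count in the primary analysis. Under protocol section 5.4 investigators know the treatment.

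**The concern.** The events that serelaxin is meant to reduce are also counted as adverse events. A lower WHF count on serelaxin therefore lowers the share of patients with any AE, any SAE or a severe AE, whatever happens to other events. The same occurs if unblinded investigators only label WHF less often on serelaxin. Blinded adjudication protects the primary analysis from that labelling, but it does not protect the AE tables. A true excess of other events would then look smaller than it is in the overall lines, which a reader is likely to look at first.

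The tables that remain do not give the missing number. One patient can have both a WHF event and another AE, so the share with any non-WHF AE cannot be found by subtraction.

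**Working it through.** **The plan's own figure.** Protocol section 1.1 gives WHF or death through Day 5 in the pivotal phase III trial as 6.5% on serelaxin and 12.0% on placebo, odds ratio 0.51. Check: (0.065/0.935) / (0.12/0.88) = 0.0695/0.1364 = 0.51. This is the only Day 5 effect size for WHF or death that the documents give. The assumptions behind this trial's sample size are blacked out.

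**Inputs.** Planned N is 3,183 at 2:1, so about 1,061 on standard of care and 2,122 on serelaxin. The non-WHF AE rate *b* is not in the documents. I assume 10% on standard of care and 13% on serelaxin, independent of WHF, which is a 3.0-point excess (z = 2.55 unpooled, about 2.46 pooled). The pivotal-trial pair counts WHF or death; the two lower WHF pairs are assumed, because the Amendment 4 rationale says primary events ran below expectation.

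**Step 1: what the overall line shows.** With WHF rate *w*, P(any event) = 1 − (1 − *b*)(1 − *w*).

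| WHF, standard of care vs serelaxin | Any event, standard of care | Any event, serelaxin | Difference shown |
|---|---|---|---|
| 6.0% vs 4.5% | 1 − 0.90×0.940 = 15.4% | 1 − 0.87×0.955 = 16.9% | +1.5 points |
| 8.0% vs 5.5% | 1 − 0.90×0.920 = 17.2% | 1 − 0.87×0.945 = 17.8% | +0.6 points |
| 12.0% vs 6.5% | 1 − 0.90×0.880 = 20.8% | 1 − 0.87×0.935 = 18.7% | −2.1 points |

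**Step 2: other background rates.** The non-WHF excess that is exactly cancelled is d* = (1 − *b*)[1 − (1 − *w*_standard)/(1 − *w*_serelaxin)]. At 12.0% vs 6.5% the bracket is 1 − 0.880/0.935 = 0.0588. So d* is 5.3 points at *b* = 10%, 4.7 at 20%, 4.1 at 30%, 3.5 at 40% and 2.9 at 50%. With WHF removed, the power to detect that same excess (two-sided 0.05) would be 99%, 85%, 65%, 48% and 35%. At half those WHF rates (6.0% vs 3.25%), d* runs from 2.6 points at *b* = 10% to 1.4 at 50%.

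**Step 3: the SAE line.** Only serious WHF counts here, and the serious share is not in the documents. For a non-WHF SAE rate of 10% and the 12.0% vs 6.5% pair, d* is 1.0, 2.6 or 5.3 points if 20%, 50% or 100% of WHF events are serious.

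**Step 4: can the non-WHF rate be recovered?** From a total of 20.8% and a WHF share of 12.0%, the share with any non-WHF AE on standard of care lies between 20.8 − 12.0 = 8.8% and 20.8%. On serelaxin it lies between 18.7 − 6.5 = 12.2% and 18.7%. The difference between arms could then be anything from 12.2 − 20.8 = −8.6 to 18.7 − 8.8 = +9.9 points. Preferred-term tables do not settle this, because the verbatim is not fixed and WHF may be coded under a symptom term.

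**The case against.** **Recording WHF as an AE is proper.** It meets the protocol's AE definition, guards against under-reporting of cardiac failure, and would show harm if serelaxin worsened heart failure. This stands: the gap is in the SAP summaries, not in the recording rule.

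**Most of the safety plan is untouched.** A reader might infer that the safety evaluation as a whole can hide harm. The documents do not support that. Hypotension, renal impairment, hepatotoxicity, hypersensitivity and other specific harms have their own tables, and AE frequency is one of several components in protocol section 6.5. No formal test of the overall lines is specified. The point is confined to three overall lines.

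**The size rests on assumptions.** A reader might expect the sign to reverse. In Step 1 that happens only at the pivotal trial's rates with a low background, and those rates include deaths. At 50% vs 53% and the same WHF rates the overall line reads 1 − 0.50×0.880 = 56.0% vs 1 − 0.47×0.935 = 56.1%, so the excess is hidden but not reversed. If patients with WHF also tend to have other AEs, the effect shrinks. Even the 2.1-point deficit has z of only about 1.4, so the table would show no clear difference rather than a safety advantage.

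**Amendment 4.** The plan records that "So far, more than two thousand three hundred and thirty (2337) patients have been randomized" when the recording rule was clarified, which is 2,337/3,183 = 73% of the target. A reader might infer a bias between arms from two reporting standards. The documents do not support this: the amendment speaks of potential under-reporting, and the change applies to both arms alike.

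**Scope of the rule.** All WHF endpoints is exact only through Day 5, because non-serious WHF after Day 5 is not collected as an AE.

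**Conclusion.** The concern holds for the overall any-AE, any-SAE and severe-AE lines. They mix investigator-reported WHF, confirmed or not, with safety, and SAP section 5.3 offers no patient-level figure without it. Under the assumed 10% vs 13% background and independence, a 3.0-point excess is reduced to 1.5 or 0.6 points at moderate WHF differences and reverses to −2.1 points only at the pivotal trial's rates. The effect requires a real or reported WHF benefit on serelaxin. It is smaller at higher background rates, with overlap between event types, and on the SAE line if few WHF events are serious. A minor asymmetry works in the same direction: treatment-emergent counting starts at randomization on standard of care but at infusion start on serelaxin, a gap that protocol section 5.5.5 puts at 30 to 60 minutes in most cases.

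**What to change.** In SAP section 5.3, beside the existing summaries, add patient-level any-AE, any-SAE and severe-AE frequencies by arm that exclude AEs matched to a WHF record:

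- Through Day 5, match on the endpoint flag plus the Clinical worsening of heart failure page. The flag alone is not enough, because it also covers death.
- For SAEs after Day 5 through Day 14, match to the Heart failure details page, where SAP section 5.2 places the later, non-adjudicated WHF events.
- Keep deaths and AEs from other causes in.

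State that the two versions are interpreted together. The version without WHF should not become the sole basis of the comparison, since that would remove any heart-failure harm from view, and the flag is itself part of open-label AE reporting. A second version of AEs leading to discontinuation is not needed, because the standard-of-care arm has no study infusion to stop.

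The cost is one SAP paragraph, a few extra tables and some record matching. The flag and both pages already exist. The match after Day 5 should be tried before database lock.

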7.1 Adverse events

An AE is any untoward medical occurrence (i.e., any unfavorable and unintended sign [including abnormal laboratory findings], symptom or disease) in a subject or clinical investigation subject after providing written informed consent for participation in the study. Therefore, an AE may or may not be temporally or causally associated with the use of a medicinal (investigational) product.

The occurrence of AEs shall be sought by non-directive questioning of the patient at each visit during the study. Adverse events may also be detected when they are volunteered by the patient during or between visits or through physical examination, laboratory test, or other assessments.

Abnormal laboratory values or test results constitute AEs only if they fulfill at least one of the following criteria:

- they induce clinical signs or symptoms,
- they are considered clinically significant,
- they require therapy.

Clinically significant abnormal laboratory values or test results should be identified through a review of values outside of normal ranges/clinically notable ranges, significant changes from baseline or the previous visit, or values which are considered to be non-typical in patients with underlying disease. Investigators have the responsibility for managing the safety of the individual patient and identifying AEs. Alert ranges for lab test abnormalities are included in [Appendix 1](#).

AEs shall be recorded in the Adverse Events eCRF under the signs, symptoms or diagnosis associated with them accompanied by the following information.

- the severity grade
 - mild: usually transient in nature and generally not interfering with normal activities
 - moderate: sufficiently significant to interfere with normal activities
 - severe: prevents normal activities
- its relationship to the investigational treatment (no/yes)
- its duration (start and end dates). If the event is ongoing, an outcome of not recovered/not resolved shall be reported.
- whether it constitutes a SAE
- action taken regarding investigational treatment

- whether other medication or therapies have been taken (concomitant medication/non-drug therapy)
- its outcome (not recovered/not resolved; recovered/resolved; recovering/resolving, recovered/resolved with sequelae; fatal; unknown)

An SAE is any AE (appearance of (or worsening of any pre-existing) undesirable sign(s), symptom(s) or medical conditions(s) which meets any one of the following criteria

- is fatal or life-threatening
- results in persistent or significant disability/incapacity
- constitutes a congenital anomaly/birth defect
- requires inpatient hospitalization or prolongation of existing hospitalization, unless hospitalization is for:
 - routine treatment or monitoring of the studied indication, not associated with any deterioration in condition
 - elective or pre-planned treatment for a pre-existing condition that is unrelated to the indication under study and has not worsened since signing the informed consent
 - treatment on an emergency outpatient basis for an event not fulfilling any of the definitions of a SAE given above and not resulting in hospital admission
 - social reasons and respite care in the absence of any deterioration in the patient's general condition
- is medically significant, i.e. defined as an event that jeopardizes the patient or may require medical or surgical intervention to prevent one of the outcomes listed above.

All malignant neoplasms will be assessed as serious under "medically significant" if other seriousness criteria are not met.

Unlike routine safety assessments, SAEs are monitored continuously and have special reporting requirements; see Section 7.2.

All AEs shall be treated appropriately. Treatment may include one or more of the following: no action taken (i.e. further observation only); investigational treatment dosage adjusted/temporarily interrupted; study drug(s) permanently discontinued; concomitant medication given; non-drug therapy given. The action taken to treat the AE shall be recorded on the Adverse Event eCRF.

Once an AE is detected, it shall be followed until its resolution or until it is judged to be permanent an assessment shall be made at each visit (or more frequently, if necessary) of any changes in severity, the suspected relationship to the investigational treatment, the interventions required to treat it and the outcome.

Information about common side effects already known about the investigational drug can be found in the Investigator Brochure (IB) or will be communicated through IB updates in the form of Investigator Notifications. This information will be included in the patient informed consent and shall be discussed with the patient during the study as needed.

The investigator shall also instruct each patient to report any new AE (beyond the protocol observation period) that the patient, or the patient's personal physician, believes might reasonably be related to study treatment. This information shall be recorded in the investigator's source documents. If the AE meets the criteria of a SAE, it must however be reported to Novartis.

7.2 Serious adverse event reporting

To ensure patient safety, every SAE, regardless of causality, occurring after the patient has provided informed consent through Day 14 must be reported to Novartis within 24 hours of learning of its occurrence. Any SAEs experienced after the 14 days period should only be reported to Novartis if the investigator suspects a causal relationship to study treatment.

Recurrent episodes, complications, or progression of the initial SAE must be reported as follow-up to the original episode, regardless of when the event occurs. This report must be submitted within 24 hours of the investigator receiving the follow-up information. An SAE that is considered completely unrelated to a previously reported one shall be reported separately as a new event.

Information about all SAEs (either initial or follow up information) is collected and recorded on the paper Serious Adverse Event Report Form. The investigator must assess the relationship to study drug, complete the SAE Report Form in English, and send the completed, signed form by fax within 24 hours after awareness of the SAE to the local Novartis Drug Safety and Epidemiology Department. The telephone and fax numbers of the contact persons in the local department of Drug Safety and Epidemiology, specific to the site, are listed in the investigator folder provided to each site. The original copy of the SAE Report Form and the fax confirmation sheet must be kept with the case report form documentation at the study site. Follow-up information shall be provided using a new paper SAE Report Form stating that this is a follow-up to a previously reported SAE.

Follow-up information shall describe whether the event has resolved or continues, if and how it was treated, whether the treatment code was broken or not and whether the patient continued or withdrew from study participation. Each re-occurrence, complication, or progression of the original event shall be reported as a follow-up to that event regardless of when it occurs.

If the SAE is not previously documented in the Investigator's Brochure or Package Insert (new occurrence) and is thought to be related to the investigational treatment, a Drug Safety and Epidemiology Department associate may urgently require further information from the investigator for Health Authority reporting. Novartis may need to issue an Investigator Notification (IN) to inform all investigators involved in any study with the same investigational treatment that this SAE has been reported. Suspected Unexpected Serious Adverse Reactions (SUSARs) will be collected and reported to the competent authorities and relevant ethics committees in accordance with Directive 2001/20/EC or as per national regulatory requirements in participating countries, except for SUSARs that are also efficacy endpoints and exempted from such expedited reporting as detailed below.

Study-specific expediting rules for SUSARs that are also efficacy endpoints

In studies such as this one, where the efficacy endpoints potentially meet the requirements for SUSAR reporting, the integrity of the study may be compromised if the endpoints are systematically expedited to competent authorities/relevant ECs and investigators. In such cases, regulations allow an exemption from SUSAR expediting aimed at ensuring the validity of an outcome study (European Commission: Communication from the Commission CT-3 (2011/C 172/01); FDA Guidance 2012). Therefore, the rules for expediting SUSARs during the 14-day SAE collection period will be applied as follows.

1. Endpoint events that will not be expedited

A SUSAR will not be expedited, if the event is considered consistent with one of the efficacy endpoints:

- From randomization through Day 5: renal deterioration (defined as ≥ 0.3 mg/dL increase in serum creatinine)
- From randomization through Day 14: in-hospital worsening heart failure (WHF) requiring rescue therapy (see endpoint definition in Section 2), or all cause death, or readmission for heart failure (HF)
- Definitions:
 - In-hospital WHF includes worsening signs and/or symptoms of heart failure that require an intensification of intravenous therapy for heart failure or assisted (invasive or non-invasive) ventilation, renal or circulatory support. Such treatment can include the institution or up-titration of IV furosemide, IV nitrates or any other IV medication for heart failure, or institution of mechanical support such as assisted (invasive or non-invasive) ventilation, ultrafiltration, hemodialysis, intra-aortic balloon pump or ventricular assist device, etc.
 - HF signs and symptoms include, but are not limited to, dyspnea on exertion or at rest, orthopnea, rales, jugular venous pulse (JVP) and peripheral edema.

In addition, Novartis will not expedite a report to competent authorities/relevant ECs and will not issue an IN.

If specifically requested by a local Health Authority, pre-specified endpoints (see above) that also meet the criteria for SUSARs will be expedited to this Health Authority. Investigator Notifications will not be issued for these events.

2. Endpoint events that will be expedited

There is a subset of SAEs, which will require expedited reporting to competent authorities/relevant ECs and investigators, if these meet SUSAR and/or endpoint criteria and are indicative of one of the following events:

- Fatal events, which are often associated with drug toxicity and which include SAEs indicative of anaphylaxis, angioedema, blood dyscrasias (including agranulocytosis, aplastic anemia, bone marrow failure, pancytopenia and bicytopenia), hepatic injury, inflammatory lung disorders (including allergic, fibrosing, necrotizing alveolitis, eosinophilic pneumonia and interstitial lung disease), rhabdomyolysis, and serious cutaneous skin reactions (including Stevens-Johnson syndrome, toxic epidermal necrolysis and erythema multiforme) torsade de pointes and prolonged QT interval.

- Efficacy endpoints, for which the investigator considers that the character and the severity of the endpoint is not consistent with the expected presentation or course of that endpoint and the investigator considers that the study drug and/or study procedures may have contributed to this abnormal presentation.

Study-specific expediting rules for SUSARs that are commonly observed in the study population

In clinical trials evaluating treatments for high morbidity and/or high mortality disease states, SAEs that are known consequences of the underlying disease or condition under investigation, or events common in the study population, are anticipated to occur with some frequency during the course of the trial, regardless of drug exposure. While the investigator must still report all non-serious AEs and SAEs through Day 5, and through Day 14, respectively, SUSARs considered consistent with the following SAE Preferred Terms (PTs) will not be reported in an expedited timeframe to regulatory agencies, ECs or investigators during the course of the study:

abdominal pain, acute coronary syndrome, acute pulmonary edema, anaemia, angina pectoris *, anxiety, arthralgia, asthenia, azotaemia, back pain, blood creatinine *, blood pressure *, blood urea nitrogen *, bronchitis *, cardiac arrest, cardiac arrhythmias (all PTs presenting any type of arrhythmia **excluding** electrocardiogram QT interval abnormal, electrocardiogram QT prolonged, long QT syndrome, torsade de pointes), cardiac asthma, cardiac failure *, cardiac output *, cardiac pacemaker *, cardiac tamponade, cardiogenic shock, cardiorenal syndrome, cerebrovascular accident, chest pain, chronic obstructive pulmonary disease, confusional state, constipation, cor pulmonale *, cough *, creatinine renal clearance *, delirium, diarrhea, dizziness, dyspnea *, ejection fraction *, fatigue, generalized oedema, glomerular filtration rate *, gout, headache, hepatic congestion, hyperglycemia, hyperkalemia, hyperlipidemia, hypertension *, hyperuricaemia, hypoglycemia, hypokalemia, hypernatremia, hypotension *, implantable defibrillator *, influenza *, insomnia, loss of consciousness, muscle spasm, musculoskeletal pain, myocardial infarction*, nasopharyngitis, nausea, edema, edema due to cardiac disease, edema peripheral, osteoarthritis, pain in extremity, pericardial effusion, pleural effusion, pneumonia *, presyncope, pulmonary hypertension, pulmonary edema, renal failure *, renal impairment, respiratory distress *, respiratory failure *, respiratory tract infection *, stroke *, syncope, transient ischemic attack, urinary tract infection, valve *, ventricular failure *, vomiting, weight increased.

*More than one PT can contain this term.

If specifically requested by a local health authority, pre-specified AEs commonly observed in the study population (see above) that also meet the criteria for SUSARs will be expedited to this Health Authority. Investigator Notifications will not be issued for these events.

